### 3.7 Exclusion criteria

Typical RBBB. No ability to give informed consent, non-cardiovascular co-morbidities with reduced life-expectancy < 1 year or patients with complex congenital heart disease.

In-hospital patients will be included during the in-hospital period and the baseline echocardiogram and BP monitoring will be performed as part of the routine clinical investigations. From the “Out-patients’ clinics the patients will be recruited after assessing ECGs from patient’s records.

In a Pilot-study feasibility of patient recruitment will be tested. The incidence of heart failure and deterioration of ventricular function in the first 100 included patients will be assessed in order to define the power of the final study-population size.

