### 3.10 Statistical power

It is unknown how high the percentage in this study population will be who suffer from deterioration of LV function. Therefore, a pilot-study on the first 100 study-subject of the different subgroups will be performed in order to calculate the power of the final population size. Pilot participants will be included into the final study population. Assuming different proportions of 5%, 10%, 20% and 30% of patients with deteriorating ventricular function, a difference in septal or global strain between at 5% at a SD of  $\pm 6\%$  the sample size needed for hypothesis 1 in each subgroup will be 220, 129, 73 or 57, respectively for a two-sided test and a Type I error of 0.05.

For calculation of hazard-ratios between patients with against without deterioration of LV function for the primary outcome variable: hospital admission due to CVD, assumed that 5% of all patients either

deteriorate function and the presence of decreased segmental work indicates at least a relative risk of 1.8, at an alpha of 0.05 with 500 patients included, the statistical power will be 82%.

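### The per-subgroup sample sizes for hypothesis 1 rest on one unsourced SD of 6 for both septal and global strain, and the pilot is not stated to check it

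*Protocol*

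**What the plan says.** Section 3.10 of the Protocol gives the reason for the pilot: "It is unknown how high the percentage in this study population will be who suffer from deterioration of LV function". It follows that "a pilot-study on the first 100 study-subject of the different subgroups will be performed in order to calculate the power of the final population size". Section 3.7 names what the pilot will look at. On recruitment it says "In a Pilot-study feasibility of patient recruitment will be tested". On outcomes it says "The incidence of heart failure and deterioration of ventricular function in the first 100 included patients will be assessed", and gives settling the power for the eventual sample as the purpose.

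The sizes for hypothesis 1 are then worked out in section 3.10: "Assuming different proportions of 5%, 10%, 20% and 30% of patients with deteriorating ventricular function", with "a difference in septal or global strain between at 5% at a SD of" 6, "respectively for a two-sided test and a Type I error of 0.05". The results are 220, 129, 73 and 57, stated as the need in each subgroup. No power is given for this calculation, and no source for the difference or the SD.

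Section 3.1 sets the whole cohort at no fewer than 1000 patients. Section 3.6 lists subgroups that include paced patients, patients with bundle branch block after acute infarction, and patients with a CRT indication. Sections 3.1 and 3.8 provide baseline echocardiography, suitable for speckle tracking, for every prospective participant.

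**The concern.** The size needed to compare mean strain between deteriorating and stable patients depends on two uncertain inputs: the share who deteriorate, and the square of the strain SD. The protocol treats the first as unknown and sets up a pilot to learn it. It states the second as a single number, without a source, for two different quantities (a regional value and a whole-ventricle value) and for every subgroup. The pilot text names event rates and feasibility, and does not mention the SD.

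If the sizes are recalculated from the observed rate alone, they carry whatever error there is in the 6. The stated sizes contain only about 11 to 17 deteriorating patients each (5% of 220 = 11; 10% of 129 ≈ 13; 20% of 73 ≈ 15; 30% of 57 ≈ 17), so there is little slack within a subgroup.

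**Working it through.** **Inputs.** From section 3.10: difference d = 5, SD s = 6, two-sided alpha 0.05, deteriorating proportion p = 5%, 10%, 20% or 30%, stated N = 220, 129, 73, 57. Assumed: a power target of 80%, because none is stated.

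**Reproducing the stated sizes.** For two means with unequal groups, N = (s/d)² × (z₀.₉₇₅ + z₀.₈₀)² / [p(1 − p)], with (1.960 + 0.842)² = 7.849 and (6/5)² = 1.44. At p = 10% this is 1.44 × 7.849 / 0.09 = 125.6, so 126. The noncentral t version adds about two patients.

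| p | Stated N | Normal formula | Noncentral t | Power at stated N, SD 6 |
|---|---|---|---|---|
| 5% | 220 | 238 | 240 | 76.5% |
| 10% | 129 | 126 | 128 | about 80% |
| 20% | 73 | 71 | 73 | about 80% |
| 30% | 57 | 54 | 56 | about 81% |

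Three of the four sizes agree with 80% power to within one patient. None of the four agrees with 85% or 90%, so 80% is a fair inference. The 220 does not agree; 80% needs 240.

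**Sensitivity to the SD.** N scales with (SD/6)²: 0.69 at SD 5, 1.36 at 7, 1.78 at 8, 2.25 at 9. SDs other than 6 are assumptions, shown as a range.

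| SD | Power at 129 (p = 10%) | N for 80%, p = 10% | N for 80%, p = 5% |
|---|---|---|---|
| 5 | 92% | 90 | 168 |
| 6 | 80% | 128 | 240 |
| 7 | 68% | 173 | 326 |
| 8 | 56% | 226 | 425 |
| 9 | 47% | 285 | 538 |

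If N is reset to the observed rate with the SD kept at 6, the resulting power does not depend on the rate, since p(1 − p) cancels. It is Φ(2.802 × 6/SD − 1.960): 92% at SD 5, 80% at 6, 67% at 7, 56% at 8.

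**Whole cohort.** With 1000 patients as one group and p = 5%, power is about 99% at SD 8, 93% at SD 10 and 82% at SD 12. It is higher at higher rates.

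**Subgroups above the stated minimum.** With 200 per subgroup (an assumption, 1000/5) and SD 8, power is about 49% at p = 5%, 76% at 10%, and 94% or more at 20% to 30%.

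**What the pilot could deliver.** The 95% chi-square limits for an SD of 6 from 100 patients are about 5.3 to 7.0, that is −12%/+16%. From 20 patients (an assumed subgroup share of the 100) they are −24%/+46%.

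**Effect of pooling over outcome status.** The pooled SD is √(s² + p(1 − p)d²). For a true 6 it is √(36 + 0.09 × 25) = 6.2 at p = 10% and √(36 + 0.21 × 25) = 6.4 at p = 30%. The bias is small and conservative.

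**The case against.** The strongest objection is that silence is not a decision. Section 3.10 says the pilot is there to calculate power and does not limit the inputs. A power calculation for a strain difference needs an SD, the pilot patients have baseline echocardiograms, and the detail could sit in an analysis plan that is not at hand. This stands as far as it goes: a reader might infer that the SD will be held at 6, and the text does not say so. But the protocol itself chooses to state the sizing inputs and the pilot's purpose, names one input as unknown, and leaves out the other.

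A reader might also infer that the pilot alone fixes the final size and that the study could be badly underpowered. The documents do not support that. Section 3.1 sets at least 1000 patients whatever the pilot shows, and at that size the whole-cohort comparison keeps about 82% power at 5% deteriorating even with an SD of 12. The exposure is within subgroups with low rates. That still counts, because section 3.10 states its sizes per subgroup.

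Nothing in the documents shows that 6 is too low. At SD 5 the stated 129 gives 92% power, so the required size could fall as well as rise.

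Nor is the SD shown to matter more than the rate. Over 5% to 30% the stated N changes by a factor of 3.9 (220/57), against 1.36 to 2.25 for SDs of 7 to 9. Giving the rate priority is reasonable; leaving the SD unmentioned is the gap.

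Finally, the pilot's 100 patients come from different subgroups, so the precision for the whole 100 does not carry over to each subgroup. This is accepted, and the fix allows for it.

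**Conclusion.** The point holds as a modest, inexpensive improvement. One unsourced SD of 6 supports the hypothesis 1 sizes for two different strain measures in every subgroup, and no check of it is stated in the pilot. Whole-cohort power is not in doubt at 1000 or more patients. Within a subgroup held at the stated 129, power moves from about 80% to 68% or 56% if the true SD is 7 or 8, and to about 92% if it is 5. These figures rest on assumed SDs, on the stated difference of 5, and on an inferred 80% target.

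One discrepancy does not depend on any assumed SD. On the protocol's own inputs, 220 at 5% deteriorating gives about 76.5% power, out of line with the other three sizes, which sit at about 80%.

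**What to change.** In sections 3.7 and 3.10:

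- State that the pilot also estimates the SD of baseline septal strain and the SD of baseline global strain, separately. Pool over outcome status, so that no comparison by outcome is made and there is no type I error cost.
- State the power target for the strain calculation.
- Recalculate the four sizes with the SD of the marker that will be tested, give a source for the provisional 6 until then, and correct the 220 (240 for 80% power at SD 6).
- Report any subgroup SD with its confidence interval, since about 20 patients fix it only to about −24%/+46%.

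The cost is one or two sentences and a recalculation from echocardiograms already planned, with no wait for the repeat visit. The downside is that the stated sizes may become less favourable.

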### 3.8 Echocardiography

Participants will be examined with transthoracic echocardiography using a commercially available system (Vingmed Vivid E9 or E95 with M4S-RS Sector Probe, General Electric Healthcare, Horten, Norway). The general echocardiography protocol, optimizing imaging loops for two-dimensional speckle tracking analyses and myocardial work analysis and the generation of wall stress-strain loops.

### 3.9 Artificial intelligence

An unsupervised AI algorithm (Multiple Kernel Learning and K-means clustering) will be used to categorize subjects by similarities in clinical parameters, LV volume, wall stress and deformation traces at rest and after hand-grip test. All available input data will be converted into a compact representation space where subjects are positioned according to their similarity. Afterwards subjects will be clustered with K-means algorithm to identify phenotypically-distinct categories patients with adverse outcomes.

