## **2 Hypotheses, aims and objectives:**

### **2.1 Primary hypotheses**

1. Typical strain-pattern and myocardial work assessment improve substantially prediction of heart failure development, hospital admission, death and adverse cardiovascular events and can help to establish more effective patient selection criteria for CRT or medical heart failure treatment.
2. AI, incorporating strain imaging and myocardial work assessment as well as conventional clinical patient characteristics is able to improve additionally risk assessment and treatment response in the LBBB population

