### 2.3 Primary objectives:

1. To identify patients with LBBB eligible for timely CRT treatment by evaluating myocardial work by echocardiography as predictors in for a) deterioration of myocardial function, b) risk for mortality, c) heart failure development and hospital admissions d) risk for MACCE
2. To investigate the ability of AI to improve risk assessment and treatment response in the LBBB population

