### 3.2 Population-based studies:

In addition to the prospective study, we intend to include retrospective data from a population-based study with echocardiography from Katholieke Universiteit Leuven, Belgium. This study has already been approved for baseline echocardiography and follow-up assessment. Participants with LBBB or PVP of the Tromsø 7 study will be invited to be prospectively included into the study-population from University Hospital of North Norway, Tromsø .

### 3.3 Planned inclusion of participants of Tromsø 7

The main focus of this study is to identify individuals with LBBB or ventricular pacing who have characteristics for stable disease or those who are soon developing clinical heart failure.

Asymptomatic Individuals with LBBB are usually not referred to the cardiologist. In order to create a suitable control-algorithm for these stable diseases and to identify individuals who present with subclinical heart failure who are in need of either medical treatment or even CRT it will be important to include the broad spectra of patients and "healthy" participants of epidemiological studies. ECG of the participants of Tromsø 7 have been analyzed and we wish to include all participants with increased QRS width >130ms and LBBB configuration or predominant ventricular pacing, excluding those with

RBBB configuration. Echocardiography in individuals with LBBB and predominant ventricular pacing is clinically indicated.

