### 3.11 Statistics

Patients with deteriorating myocardial function will be identified by increasing proBNP by more than 10%, increasing NYHA class, increasing diastolic volume by more than 10% and/or decreasing EF by more than 5%. ANOVA will be used to compare parameters between patients with deteriorating myocardial function and those with unchanged clinical condition after one year. ROC curve analysis will serve to find the ideal cut-off values for continuous variables and assessing sensitivity and specificity of the tests. Univariate and multivariate logistic regression tests will be performed in order to identify the most powerful parameters predicting development of heart-failure with hospital admissions as primary outcome and predicting death (or transplantation) as secondary outcome.

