### 3.12 Data management

Data from patient's visit and patient's journal will be stored as de-identified data in an a password secured internet-based database (Viedoc). Viedoc is approved by The Norwegian Data Protection Authority for use in scientific studies. Echocardiographic data will be stored as de-identified DICOM files including locally performed measurements, labeled by the patient's study ID, all ECGs will be taken in digitalized format and be stored as de-identified image files as well as DICOM files. All de-identified files will be locally stored at a dedicated server. Key files coupling personal patient information to ID's will be stored locally on a server with restricted access. All de-identified ECGs, echocardiography-studies and key-files will be centrally collected at University Hospital of North Norway, Tromsø, latest after end of the second patient's visit. Echocardiographic data will be analyzed in the core-lab at University Hospital of North Norway, Tromsø. Readers of the strain-data will be blinded for the outcome-data. Other researchers assess outcome-data from NPR and The Norwegian Cause of Death Registry will be added to the database. The de-identified dataset and DICOM images from echocardiography and ECG will also be transferred to NTNU Trondheim for automated reading of the echocardiographic imaging and AI purposes.

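### Primary hypothesis 2 says AI improves risk assessment and treatment response, but the AI method described is clustering with no link to a conventional model or a treatment contrast

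*Protocol*

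**What the plan says.** Section 2.1 states, as the second primary hypothesis, that AI combining strain, myocardial work and conventional patient characteristics "is able to improve additionally risk assessment and treatment response in the LBBB population". Section 2.3 repeats this as the second primary objective: "To investigate the ability of AI to improve risk assessment and treatment response in the LBBB population".

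Section 3.9 gives the method: "An unsupervised AI algorithm (Multiple Kernel Learning and K-means clustering) will be used to categorize subjects by similarities in clinical parameters". The remaining inputs are deformation traces, wall stress and LV volume. The stated purpose is: "Afterwards subjects will be clustered with K-means algorithm to identify phenotypically-distinct categories patients with adverse outcomes". The section names no reference model, no measure of improvement and no treatment comparison.

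Section 3.11 plans regression and ROC work, but for individual measurements: "Univariate and multivariate logistic regression tests will be performed in order to identify the most powerful parameters predicting development of heart-failure", and "ROC curve analysis will serve to find the ideal cut-off values for continuous variables". It does not mention the clusters. Section 3.10 sizes hypothesis 1 and a hazard-ratio comparison, and gives nothing for hypothesis 2. Section 3.12 mentions data transfer "for automated reading of the echocardiographic imaging and AI purposes" and describes no analysis.

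**The concern.** A claim that AI improves risk assessment further is comparative: it needs something to improve on. The method in 3.9 is not comparative. It sorts patients by similarity and then looks at which groups fare badly.

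Clinical parameters and LV volume go into the clustering, so clusters are likely to follow risk factors that clinicians already use. Such clusters will differ in outcome even if they add nothing to those risk factors. A reader following 3.9 could then report a primary hypothesis as supported by groups that predict worse than the clinical variables they were built from.

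Treatment response has a separate gap. Section 3.9 contains no contrast between treated and untreated patients. Section 3.5 lists CRT implantation as an outcome, and 3.1 describes an observational cohort. Different event rates between clusters say nothing about who responds to CRT.

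**Working it through.** The protocol gives no sample size, power or error rate for hypothesis 2, so there is no figure to reproduce. Two questions can be checked.

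**Inputs from the protocol.** N is at least 1000 (3.1). Rates of deterioration are 5%, 10%, 20% and 30% (3.10). **Assumed, because the protocol does not give it:** the number of clusters K.

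**1. Does a difference in outcome between clusters show improvement?**

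Set-up (assumed): N=1000, K=4, outcome driven by two clinical variables, clusters carrying no information beyond those two, 200 runs. Two likelihood-ratio tests at 5%:

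- Without a comparator: 2 × (logL[clusters] − logL[intercept only]), on K−1 = 3 degrees of freedom.
- With a comparator: 2 × (logL[clinical + clusters] − logL[clinical]), on 3 degrees of freedom.

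| Question asked | Runs declared positive |
|---|---|
| Do clusters differ in outcome? | 100% |
| Do clusters add to the clinical model? | about 4-5% |

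The clusters had an AUC of 0.66 and the clinical model 0.72. So the clusters looked prognostic every time while discriminating less well than the variables behind them. With 200 runs, the standard error of a 5% rate is √(0.05 × 0.95 / 200) = 0.015, so 4% and 5% are the same result.

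**2. What can chance produce if a cluster is singled out after outcomes are seen?**

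Set-up: K equal clusters with the same true risk, 20,000 draws, N=1000. The ratio is the highest cluster rate divided by the mean rate of the other K−1 clusters. Median ratio:

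| Event rate | K=3 | K=5 |
|---|---|---|
| 5% | 1.31 | 1.47 |
| 10% | 1.21 | 1.32 |
| 20% | 1.13 | 1.20 |
| 30% | 1.10 | 1.15 |

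These medians show how large the top-ranked cluster looks under no effect. They are not false-positive rates. Those were computed separately, again with clusters unrelated to outcome, N=1000, K=3 to 10 and event rates 5-30%:

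| Way of testing | False-positive rate |
|---|---|
| One omnibus test, Σ(xₖ − nₖp)² / [nₖp(1−p)] on K−1 df | 4.5-5.2% |
| Some cluster significantly higher than the rest | 6-30% |
| Some cluster different from the rest, either direction | 11-40% |
| Highest against lowest, chosen after seeing outcomes | 12-65% |

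The inflation comes from selecting clusters after the fact, not from K-means.

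**The case against.** Section 3.9 fixes the algorithm, not how its output is tested. Cluster membership could enter the multivariable logistic models of 3.11 without contradicting anything, and the protocol nowhere says there will be no comparator. The number of clusters, the covariates of a reference model and the validation scheme are commonly left to an SAP, which is not available here. This stands: the absence of those details is not the finding. What remains is that the protocol itself fixes a comparative primary hypothesis and pairs it with a method that makes no comparison. An SAP that carried out 3.9 and 3.11 literally would not test hypothesis 2.

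A reader might infer three stronger points that the documents do not support:

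- **That a high-risk cluster will be found by chance.** Some cluster always ranks highest, but a nominally significant one is a raised probability, not a certainty, and one prespecified omnibus test stays near 5%.
- **That the worst cluster is picked after outcomes are seen.** Section 3.9 lists no outcome among the inputs and states no selection rule. The closing phrase about adverse outcomes allows that reading but does not require it.
- **That AI as planned cannot answer the hypothesis.** That is true of clustering alone. Clusters tested on top of a clinical model could answer the risk-assessment part; the protocol does not say this will be done. Section 3.12 also refers to further AI work without detail.

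**Conclusion.** The mismatch is real and worth correcting. Primary hypothesis 2 and primary objective 2 assert an improvement, the described method is non-comparative, and 3.11 does not supply the link. A difference in outcome between clusters would not be evidence for the hypothesis: in the scenario tested it appeared in 100% of runs when the true added value was nil, against about 4-5% with a nested comparison. That contrast rests on K=4, N=1000 and two risk factors, all but N assumed. The 100% depends on risk factors strong enough to give an AUC of about 0.72; weaker ones would lower it.

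The chance ratios of 1.10-1.31 (K=3) and 1.15-1.47 (K=5) matter only if clusters are chosen after outcomes are seen, which the protocol does not state. They are a secondary reason to fix the test in advance. For treatment response, nothing described addresses the claim, and the cohort design limits what any later analysis could show.

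**What to change.** In 3.9, state that clusters are formed from baseline data only and without outcomes. The section speaks of all available input data, while 3.1 has echocardiography with hand-grip at baseline and at follow-up, so the present text leaves this open.

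In 3.11, state that hypothesis 2 is tested by comparing a prespecified conventional clinical model (for example age, EF, QRS, NYHA class and comorbidity) with the same model plus cluster membership or the learned coordinates. Report the internally validated change in AUC, together with calibration. The number of clusters, chosen without outcome data, and the validation scheme can be left to the SAP.

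Treat any cluster-by-CRT analysis as exploratory, because CRT is not randomised, and word the treatment-response part of hypothesis 2 to match.

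If the sponsor prefers not to make the comparison, label the clustering exploratory and do not use it to support hypothesis 2.

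Cost: a few sentences and a modest amount of further analysis, with no new data collection. The drawback is that the AI claim may prove weaker than hoped.

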### 3.10 Statistical power

It is unknown how high the percentage in this study population will be who suffer from deterioration of LV function. Therefore, a pilot-study on the first 100 study-subject of the different subgroups will be performed in order to calculate the power of the final population size. Pilot participants will be included into the final study population. Assuming different proportions of 5%, 10%, 20% and 30% of patients with deteriorating ventricular function, a difference in septal or global strain between at 5% at a SD of  $\pm 6\%$  the sample size needed for hypothesis 1 in each subgroup will be 220, 129, 73 or 57, respectively for a two-sided test and a Type I error of 0.05.

For calculation of hazard-ratios between patients with against without deterioration of LV function for the primary outcome variable: hospital admission due to CVD, assumed that 5% of all patients either

deteriorate function and the presence of decreased segmental work indicates at least a relative risk of 1.8, at an alpha of 0.05 with 500 patients included, the statistical power will be 82%.

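### The sample size of 220 for the 5% deterioration scenario does not fit the other three: at the 80% power they imply, 5% needs 240, and 220 gives 76.5%

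*Protocol*

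**What the plan says.** Section 3.10 of the protocol says that the share of patients whose LV function will deteriorate is unknown, and that a pilot on the first 100 subjects will inform the final size. Meanwhile it gives four scenarios: "Assuming different proportions of 5%, 10%, 20% and 30% of patients with deteriorating ventricular function". The effect is described as "a difference in septal or global strain between at 5% at a SD of" 6%. The result is "the sample size needed for hypothesis 1 in each subgroup will be 220, 129, 73 or 57, respectively for a two-sided test", with the error rate given as "for a two-sided test and a Type I error of 0.05".

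No power is stated for this calculation. The 82% later in the section belongs to a separate calculation, with a relative risk of 1.8 and 500 patients.

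**The concern.** All four sizes come from the same difference, SD and alpha; only the proportion deteriorating changes. They should therefore share one power. Three of them do, at 80%, and the 5% figure does not.

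The 5% scenario is the least favourable of the four and sets the largest number per subgroup. If the pilot showed deterioration near 5%, a reader would take 220 from this list. Each subgroup sized that way would then have less power than the other scenarios offer, and nothing in the text would show it.

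**Working it through.** **Inputs (section 3.10).** Difference 5 and SD 6, so the standardised difference is d = 5/6 = 0.833. Two-sided alpha 0.05. Proportion deteriorating p = 0.05, 0.10, 0.20, 0.30, so the group sizes are Np and N(1−p). No dropout is stated. Assumption: 80% power, because the protocol gives none here.

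**Formula.** For two means with unequal groups, the normal approximation is

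N = (1.960 + 0.842)² × (6/5)² / [p(1−p)] = 7.849 × 1.44 / [p(1−p)] = 11.30 / [p(1−p)].

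The t-test column below uses the noncentral t distribution with pooled variance, N − 2 degrees of freedom and noncentrality d × √[N p(1−p)]. Group sizes may be fractional.

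| p | Stated N | N for 80%, normal | N for 80%, t-test | Power at stated N, t-test |
|---|---|---|---|---|
| 10% | 129 | 125.6 | 128 | 80.5% |
| 20% | 73 | 70.6 | 73 | 80.2% |
| 30% | 57 | 53.8 | 56 | 80.9% |
| 5% | 220 | 237.9 | 240 | 76.5% |

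The t-test at 80% power reproduces three stated figures to within one patient. The fourth misses by 240 − 220 = 20, and 20/220 = 9%.

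**Power at 220 by hand (normal approximation).** 5% of 220 is exactly 11, leaving 209. N p(1−p) = 220 × 0.0475 = 10.45. Then 0.833 × √10.45 = 2.694, and 2.694 − 1.960 = 0.734, which gives 76.9%. The t-test gives 76.5%.

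**A check that assumes no particular power.** With difference, SD and alpha fixed, N p(1−p) should be nearly constant across scenarios for any given power:

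- 129 × 0.09 = 11.6
- 73 × 0.16 = 11.7
- 57 × 0.21 = 12.0
- 220 × 0.0475 = 10.45

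The small rise from 11.6 to 12.0 is what the t-test's falling degrees of freedom would produce. The 5% figure breaks the pattern. Had 76.5% been the intended power, the other three sizes would have been 118, 67 and 52.

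**Can another method give 220?** For p = 5% at 80% power, a one-sided test gives 187, a Mann-Whitney adjustment (factor π/3) 249, and a Welch test with whole patients 280. A two-sided t-test or its normal approximation gives 272 to 280 at 85% power and 319 to 340 at 90%. None gives 220.

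**Can rounding give 220?** With 11 deteriorating patients, 80% cannot be reached however many others are added. In the limit, 0.833 × √11 − 1.960 = 0.804, which gives 78.9%. Twelve are needed, and 12/0.05 = 240, with power 80.0%. Taking 12 and 208 does total 220 and gives 79.8% (t-test) or 80.2% (normal), but 12/220 = 5.45%, not 5%.

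**The case against.** The arithmetic is not in dispute; its weight is.

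- **The 80% is inferred.** This stands. That 240 is the right figure is conditional on 80%; that 220 disagrees with its neighbours is not.
- **The gap is one expected deteriorating patient, 11 against 12.** True. In a cohort that number is random: its binomial SD is √(220 × 0.05 × 0.95) = 3.2. Moving to 240 therefore does not guarantee 80% in the event. The same holds for all four scenarios, so it does not explain why one was computed differently. A rounding slip is a plausible origin for 220, but rounding the small group up does not reproduce 129.
- **The contrast is less clean in whole patients.** Also true. A total of 129 gives 77.9% with 12 and 117 or 80.7% with 13 and 116; 73 gives 79.0% with 14 and 59 or 81.0% with 15 and 58. Those totals straddle 80% because 10% of 129 and 20% of 73 are not whole numbers. At 5%, 220 splits exactly into 11 and 209 and lies at 76.5%.
- **No recruitment target is set at 220.** This stands. The four sizes are scenarios ahead of the pilot, and section 3.1 aims for at least 1000 patients overall. The hazard-ratio paragraph also assumes 5% but uses 500 patients, so the error does not carry over to it.

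These points limit the consequence. They do not make 220 correct.

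**Conclusion.** The concern holds. Under section 3.10's own inputs, 220 is inconsistent with the 129, 73 and 57 beside it. At the 80% power those three imply, the 5% scenario needs 240; at 220 the power is 76.5%, a shortfall of 3.5 percentage points. This rests on a two-sample comparison of means with common SD, no dropout, and groups split exactly in the stated proportions. The 80% target is an inference from three of the four figures, whereas the finding that no single power fits all four needs no such inference. It is a plain error in a stated sample size with a modest effect, and it does not threaten the design.

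**What to change.** In section 3.10, either restate the 5% figure as 240 and write 80% power beside the four sizes, or keep 220 and state that its power is about 76% while the other three have about 80%. If the sponsor intended a power other than 80%, state it and recompute all four sizes. The cost is one number and one phrase. The target of at least 1000 patients, the endpoints and the tests stay as they are.
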